**Study Logistics** This study began in the 2018-19 school year and will run for 7 years. All human subjects will come from 12 middle schools. To be eligible for the study, schools should be in the geographical Central Appalachia catchment area in southwest Virginia, have approximately 80 to 200 students in the 7th grade, and have an 8th grade within the same school building. The latter eligibility criteria is in effort to promote student retention at the 19-month data point. We have identified at least 22 schools that meet this criteria. If more schools are needed, we can also extend our catchment area in Central Appalachia, including to qualified schools in West Virginia.

A key intent of our design is to allow schools equal opportunity to benefit, regardless of randomized treatment allocation. For pragmatic reasons, we are not proposing a simple randomization approach in which all 12 schools (clusters) are randomized at the out-set of the study. Due to turnover in administration/teachers and fluctuations in resources, our school informants indicated it is unrealistic for a school to enter into an agreement for a research project that is as far as 3-4 years out. Therefore, to promote sound randomization and school retention, we propose to recruit and randomize 4 schools [2 Intervention Schools (IntS) and 2 Control Schools (ConS)] in 3 separate blocks. Among Intervention Schools (IntS), both students and parents complete the evaluation components and receive Kids SIPsmartER. In Control Schools (ConS), both students and parents only complete the evaluation components, they do not receive the Kids SIPsmartER program. Control schools become Delayed Intervention Schools (DIntS) schools in the following academic year and receive the Kids SIPsmartER program (See Attachment in Study Overview file).

[MODIFICATION August 10 2021]: Throughout the execution of in-person study activities, researchers will abide by current UVA policy regarding masks as well as any school-level policies that exceed UVA policy.

Within each block of our stepped wedge design, we will use pure randomization. IntS and Delayed Intervention Schools (DIntS) are co-delivered by researchers and 7th grade teachers, whereas Support Schools (SupS) and Organizational Maintenance (OrgM) School are delivered by 7th grade teachers. Student and caregiver individual-level data is collected during IntS, DIntS, ConS and

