SupS years, but not OrgM years. The primary 7-month SSB outcome is completed by May 2021. Individual-level 19-month maintenance data is collected as students matriculate into 8th grade. Implementation indicators are tracked in IntS, DIntS, and SupS years.

There will be 30 cohorts of students and parents/guardians in the 12 schools: 6 Intervention cohorts, 6 Delayed Intervention cohorts, 12 Supported cohorts, and 6 Control cohorts.

In each school's first year of implementation, Kids SIPsmartER will be co-delivered by researchers and ~24 teachers. In the school's second year of implementation, teachers will be trained and supported to deliver Kids SIPsmartER with reduced in-class support. We anticipate enrolling ~3420 students and ~3180 parents/guardians. The ~24 teachers and 12 principals will also be research participants.

Additional funding to support the implementation and evaluation of Kids SIPsmartER in three of the middle schools was awarded through a Virginia Foundation for Health Youth (VFHY) grant. This grant was secured with support from the school district office that oversees these three Block 1 schools. Due to this additional funding, these middle schools will continue to receive support and engage in delivery and data collection activities, instead of going into the OrgM years (limited support, no evaluation). We are calling these years Continued Support Schools (SupS2).

It is important to note, that as surveys and curriculum activities will be during a normal class period, all students, regardless of consent, will participate in the classroom component. However, height/weight data will only be recorded for research purposes from students with parental consent and student assent to participate in this research. Furthermore, only data from consented/assented will be used for research purposes.

Kids SIPsmartER program:

Kids SIPsmartER is a multi-level intervention that uses both individual- and micro-level strategies to target students and their parents/guardians. For this R01, Kids SIPsmartER will be a 12 session, 6-month program with an integrated two-way short service message (SMS) strategy to engage parents/guardians in SSB role modeling and supporting home SSB environment changes. See Attachment in Study Overview for the program student curriculum and parent SMS messages. The parent consent and child assent processes, as described in more detail below, will occur prior to any other study activities.

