Students (SupS2). In these schools, students will complete the survey instruments at 3 time points - [baseline, 3-, 7- (immediately post program)] [AMENDMENT JULY 2021] The baseline and immediately post surveys will be shorter versions of the survey collected during IntS, DIntS, and SupS. (See below for more details) At 3-months, only self-reported SSB behaviors will be assessed.

MODIFICATION 3/16 DUE to coronavirus and school closure: We are requesting a modification to allow for flexibility in working with each of our enrolled schools to distribute and collect student surveys for our primary outcome data point. There will be no change to the content of the survey, but the student survey may be distributed and returned via mail or via an on-line Qualtrics links (using UVA Qualtrics Research Suite) sent to the students. Knowing that each school and student's within schools will have different capabilities for an on-line survey, we will work closely with each school to follow their recommendations.

Students (focus group subset) Within each school during the first two years of intervention delivery, a sub-set of students (n~20) will take part in focus groups after the completion of Kids SIPsmarter. It is expected that there will be two focus groups (~8-12 students) per intervention, delayed intervention, and support school. Focus groups will be one class period long (40-50 minutes), and students will be pulled from their normal classes to be part of the focus group. Teachers will help research staff identify the best times for the focus groups. Focus groups will assess students' satisfaction with the program and what they think could be done to make it better. Focus groups will be run by one or two trained researchers.

Parents/guardians: For parents/guardians enrolled in IntS, DIntS, and SupS schools, survey packets will be sent home from school to those who have signed consent to participate in the research at 3 times (baseline, 7- and 19-months).

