**Describe this Data Source.**

Parents/guardians (Cons, IntS, DIntS, SupS). Survey packets will be sent home from school to those who have signed consent to participate in the research at 3 times (baseline, 7- and 19-months).

The measurement packets are the same regardless of intervention or control schools. With the exception of intervention school participants answering questions about their experience with the Kids SIPsmartER program.

See Attachment #3. Data consists of:

Beverage Behaviors, including SSBs (BEV-Q)  
 SSB Theory of Planned Behavior  
 SSB Media Literacy  
 Health Literacy, 3-items valid for self-administration  
 Public Health Literacy  
 Quality of Life  
 SSB Home Environment  
 SSB Parenting Practices/Rules  
 Satisfaction Questions

MODIFICATION 3/16 DUE to coronavirus and school closure: We are requesting a modification to allow for flexibility in working with each of our enrolled schools to distribute and collect parent surveys. The caregiver survey may be distributed and returned via mail or via an on-line Qualtrics links (using UVA Qualtrics Research Suite) sent to the parents via either text or email. The only change to the survey Attachment #3 will be an addition of a current mailing address so that the gift card can be mailed directly to the parent, instead of going home with the student via school.

The changes the survey instrument have been changed and tracked, see:

View File: KSS\_IRB\_Attachment3\_CaregiverPacket\_v3\_SUBMITTED\_mod5\_add mailing address.docx

Parents/guardians (SupS2). Parents/guardians enrolled during in SupS schools will not complete survey packets.

**Will a recording device (e.g. audio, video, photographic) be used to collect data/materials from participants?** No

**Are the participant's identifying information included as part of the data at any time?** Yes, and participant identifiers will NOT retained

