### ***Secondary effectiveness, maintenance and reach outcomes***

The analytical model for the primary aim will be modified to assess these aims by making the secondary student outcomes the dependent variables. For nonlinear outcomes, such as discrete health literacy classification, appropriate link functions will be used in the multilevel model. Also, the time indicator in the model will be changed to examine effectiveness at 3-month, 7-month, and 19-month. For caregivers' outcome analysis, a simplified version of the above multilevel mixed effect selection models will be applied, recognizing the class nesting will not be of concern for this level. Furthermore, an additional indicator that signals the uptake of the SMS will be added to the model to examine the adoption of SMS influence on caregivers' behavior and home environment changes. To further explore student-caregiver dynamics, mixed effect structural equation models will examine the causal relationship among caregiver and student SSB outcome changes. Finally, differences in student effectiveness data will be explored by comparing student level changes within schools when Kids SIPsmartER is co-delivered by researchers-teachers versus when delivered by teachers only.

The program reach at student and caregiver levels will be analyzed following recommendations of Glasgow and colleagues. Participation rate at each school will be determined by dividing the total number of 7th grade students and caregivers enrolled by the total number eligible to enroll. Representativeness will be assessed by comparing demographics of students and caregivers eligible and enrolled to the demographic data provided by schools. Uptake/utilization of SMS among caregivers will also be analyzed.

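### The SAP calls an exploratory caregiver-student path causal, but randomisation does not identify that path and the SAP states no assumptions that would

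*SAP*

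**What the plan says.** The SAP's section on secondary effectiveness, maintenance and reach outcomes opens the analysis with "To further explore student-caregiver dynamics" and then states that "mixed effect structural equation models will examine the causal relationship among caregiver and student SSB outcome changes". Nothing further is specified for this model: no path diagram, direction, time ordering, role for treatment arm, confounder list or sensitivity analysis.

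The Study Logistics part of the protocol's Study Overview describes the randomisation. The team will "recruit and randomize 4 schools [2 Intervention Schools (IntS) and 2 Control Schools (ConS)] in 3 separate blocks". In intervention schools "both students and parents complete the evaluation components and receive Kids SIPsmartER"; in control schools "both students and parents only complete the evaluation components, they do not receive the Kids SIPsmartER program". The programme is described as "a multi-level intervention that uses both individual- and micro-level strategies to target students and their parents/guardians".

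On timing, caregiver "survey packets will be sent home from school to those who have signed consent to participate in the research at 3 times": baseline, 7 and 19 months. Students are surveyed at those three waves and also, for beverage behaviours only, at 3 months (Student Assessment Packet, under Data Sources). Caregiver and student records are linked within households.

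Under the primary effectiveness aim, the SAP says its models control unobserved effects that do not change over time at student, class and school level, common time and block effects, and covariates chosen a priori but not named. It does not say whether the structural equation model inherits these controls.

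**The concern.** A randomised trial supports causal statements about what was randomised. Here that is the whole package, by school. How far a caregiver's change moves the student's change is a question about two post-randomisation variables, and randomisation does not answer it. The answer has to come from assumptions about direction, lag and shared causes, and the SAP names none.

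What is at stake is the wording of a conclusion. Followed as written, the plan would let a significant path be reported as caregivers' change causing students' change, when shared influences or the reverse direction could equally have produced it.

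**Working it through.** The documents give no figure for this model, so there is none to reproduce. The check has two parts.

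**1. Identification.** Take student change S, caregiver change C and arm T over one interval:

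- S = aT + βC + e₁
- C = bT + γS + e₂, with cov(e₁, e₂) = ψ

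There are seven unknowns: a, b, β, γ, two residual variances and ψ. Given arm, the data supply five moments: two arm differences, two variances and one covariance. The model is two restrictions short. Setting a = 0 would make arm an instrument for C, but the curriculum acts on students directly. Setting b = 0 fails in the same way, because the newsletter and texts act on caregivers directly. Setting γ = 0 and ψ = 0 identifies β. Setting β = 0 and ψ = 0 identifies γ and fits equally well, so model fit cannot choose the direction.

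**2. Size of the risk when β = 0.**

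Inputs from the documents:
- 12 schools, 6 per condition; type I error 0.05; ICC 0.01; student effect 0.3 SD (SAP, Power calculation and sample size).
- About 3180 caregivers in 30 cohorts (protocol, Study Overview): 3180/30 = 106 per cohort. With the SAP's 10% student attrition applied to pairs, 106 × 0.9 = 95.4, taken as 95 per school.

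Assumptions, not in the documents:
- 50 pairs per school as a lower value.
- The same 0.3 SD effect on caregiver change; two-sided testing; independent school effects for the two members.
- Within-household correlation r from a shared cause that varies over time: 0 to 0.20. Alternatively r = 0 and a reverse path γ of 0.1.

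S was regressed on C and arm with cluster-robust standard errors (t, 11 df), as a single-equation stand-in for the model's path, with 1,500 runs per scenario. Monte Carlo error is at most √(0.25/1500) = 1.3 percentage points.

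Expected path with arm in the model: cov(S,C)/var(C) = r, or γ/(1+γ²) = 0.1/1.01 = 0.099 under reverse influence. Without arm, the common treatment effect adds 0.3² × 0.25 = 0.0225 to both numerator and denominator, so r = 0 gives 0.0225/1.0225 = 0.022.

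| True caregiver-to-student effect = 0 | Mean path, 50 / 95 pairs | Rejection, 50 / 95 pairs |
|---|---|---|
| r = 0, arm in model | 0.00 / 0.00 | 4.8% / 5.5% |
| r = 0.05, arm in model | 0.052 / 0.049 | 21.8% / 33.1% |
| r = 0.10, arm in model | 0.101 / 0.101 | 61.6% / 87.1% |
| r = 0.20, arm in model | 0.200 / 0.200 | 99.3% / 100% |
| Reverse path 0.1, arm in model | 0.100 / 0.100 | 61.3% / 85.9% |
| r = 0, arm left out | 0.022 / 0.022 | 6.6% / 10.2% |

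Hand check at r = 0.10: SE ≈ √((1−r²)/N). For N = 12 × 50 = 600, SE = 0.0406 and z = 2.46; power ≈ Φ(2.46 − 2.20) = 0.60. For N = 12 × 95 = 1140, SE = 0.0295 and z = 3.39; power ≈ Φ(3.39 − 2.20) = 0.88. Both agree with the simulation.

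**The case against.** The strongest reply is that this is one exploratory sentence, introduced as such, whose verb is only to examine. Neither the primary outcome nor the randomised secondary comparisons depend on it. That stands, and it sets the severity.

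Several stronger readings are tempting, but the documents do not support them:

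- **That the SAP plans to model simultaneous changes.** It gives no timing. The shared waves, and the students' extra 3-month survey, would allow a lagged model.
- **That a causal path can never be identified.** It is not identified by randomisation alone. Strong assumptions, if stated, could support a causal reading.
- **That any shared household factor creates the bias.** Stable household traits with constant effects largely drop out of change scores. The risk comes from shared causes that vary over time, or from reverse influence.
- **That a false finding is close to certain.** This depends on the assumed correlation: 22-33% at 0.05, and nominal at zero.
- **That the path would drive scale-up or show that texting works.** The protocol ties scale-up to student effectiveness and school-level implementation, and the SAP examines SMS uptake through a separate indicator in the caregiver model.

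What the reply does not answer is the stated target. Calling an analysis exploratory does not make its estimand causal, and controlling effects fixed over time leaves time-varying causes and reverse influence untouched.

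**Conclusion.** The concern holds as a minor point. The SAP sets a causal target for a path that randomisation does not identify, and it states no direction, lag or assumption to fill the gap. With a true caregiver-to-student effect of zero, the chance of a significant path runs from about 5-6% with no shared time-varying cause to 62-87% at a within-household correlation of 0.10 and 99-100% at 0.20. A reverse path of 0.1 alone gives 61-86%. These sizes rest on assumed correlations, an assumed caregiver effect, 50 to 95 pairs per school and a single-equation approximation. The identification argument does not depend on those numbers.

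**What to change.** In the SAP's section on secondary effectiveness, maintenance and reach outcomes:

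1. Describe the target as the association between caregiver and student changes, not a causal relationship.
2. Include arm as a predictor of both outcomes.
3. Report both directions.
4. State that no claim about the separate effect of the caregiver component will be drawn from this model.

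If causal wording is kept, pre-specify the path diagram, direction and lag, the confounders, and a sensitivity analysis for unmeasured time-varying confounding. A cross-lagged model on the waves already collected is optional. It clarifies time order but leaves time-varying household confounding in place, so it does not by itself justify causal wording.

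The cost is a few lines of SAP text and modest analysis time, with no new data. The downside is a weaker stated conclusion for one exploratory analysis.
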